2.1 Primary Objectives

The primary objective is to determine, for the patients with baseline CIS:

- The proportion that achieves a CR after treatment with inodiftagene vixteplasmid

2.2 Secondary Objectives

The secondary objectives are to determine the:

- Proportion of patients with absence of high-grade recurrent or persistent disease at 48 weeks (overall population and subgroup of patients with CIS)
- Proportion of patients with absence of high-grade recurrent or persistent disease at 12, 24, 36, 72, and 96 weeks (overall population and subgroup of patients with CIS)
- Time to recurrence (Kaplan-Meier plot)
- Proportion of patients who are progression-free at 48, 72, and 96 weeks
- Overall survival of patients enrolled in the study at 48, 72, and 96 weeks
- Quality of life in patients treated with inodiftagene vixteplasmid
- Assessment of safety

This document is confidential.

3. Study Design

3.1 Overall Study Design

This study, BC-819-18-204 (referred to as Study 204), is a Phase 2, open-label, monotherapy, single-arm, multicenter clinical trial of BC-819 (inodifitogene vixteplasmid) in patients with NMIBC adequately treated with BCG whose disease is BCG-unresponsive according to the FDA guidance ([FDA 2018](#)). Patients with BCG-unresponsive disease have NMIBC that is unlikely to benefit from and should not be treated with further intravesical BCG.

Patients are to have recurred or progressed after adequate treatment, had BCG-unresponsive disease, had a TUR, and then had all papillary disease completely resected and obvious CIS disease fulgurated when indicated. Patients with T1 disease should undergo resection of the base of the lesion when possible (biopsy should contain muscle fiber). Patients must have 1 or more of the following: completely resected high-grade T1 disease, CIS disease, or completely resected high-grade Ta disease. There is no intravesical or medical standard of care for this patient population, and the usual course is radical cystectomy.

A total of 140 patients who meet study entry criteria will be enrolled and treated during the approximately 15-month enrollment period. The first 35 patients enrolled and treated must have CIS (with or without papillary disease). After these 35 patients are treated and 10 complete responders are documented, the enrollment will expand to also allow patients with papillary disease only who meet inclusion and exclusion criteria. It is estimate that a total of approximately 70 to 100 patients with CIS will be treated.

All enrolled patients will enter the 10-week induction phase and begin treatment with BC-819. Treatment should begin within 7 days of enrollment and ≤42 days from the last TUR or biopsy. During the induction phase, patients will receive an intravesical instillation of BC-819 at a dose of 20 mg/50 mL aqueous solution once per week for 10 weeks according to the induction phase treatment schedule (see

This document is confidential.

Table 1).

Upon completion of the induction phase, patients will continue with maintenance therapy of BC-819 every 3 weeks beginning at Week 12 (Visit 11) and continuing for the next 84 additional weeks until the end of the study, defined as completion of the 96-week visit (Visit 39).

During the study, patients will undergo repeat direct visualization (ie, cystoscopy ± biopsy and cytology) and re-TUR (as needed for cause) every 12 weeks during the first and second year. Patients with persistent CIS which does not resolve by the 12-week assessment, or at subsequent 12-week assessments, or who have recurrence or new evidence of CIS or high-grade papillary disease at any time will be discontinued and classified as nonresponders and recurrences in the primary and secondary endpoint analyses. Patients benefiting from treatment, with no documented high-grade recurrence or progression, will continue to receive maintenance therapy every three weeks. Appearance or persistence of lower grade tumors will not be considered as recurrence for the primary and secondary endpoint analyses, and patients with only low-grade tumors should continue treatment after resection and histological confirmation.

This document is confidential.

4. Schedule of Assessments

The administration of BC-819 is separated into 2 phases, the induction phase and the maintenance phase.

During the induction phase, eligible patients will receive BC-819 once per week for 10 consecutive weeks.

The flow chart for the induction phase is

This document is confidential.

Table 1.

During the maintenance phase, patients will transition to once every 3 weeks administration of BC-819 and will be evaluated every 12 weeks by cystoscopy for staging of response in order to determine continued participation. The urine cytology and cystoscopy must be completed within 14 days prior to the next administration of BC-819 and fully evaluated before initiating the treatment. The flow charts for the maintenance phase are Table 2 and Table 3.

This document is confidential.

Table 1 Induction Phase

Visit	Screening	V1	V2	V3	V4	V5	V6	V7	V8	V9	V10
Day	≤42 days before V1	1	8	15	22	29	36	43	50	57	64
Baseline only procedures	X										
Interim physical examination including ECOG performance status	X	X	X	X	X	X	X	X	X	X	X
Vital signs	X	X	X	X	X	X	X	X	X	X	X
Complete blood count and biochemical profile	X										
Urine sample for urinalysis (routine and microscopic)	X										
Urine sample for culture and sensitivity	X										
Urine sample for cytology	X										
Adverse events	X	X	X	X	X	X	X	X	X	X	X
Prior and concomitant medications	X	X	X	X	X	X	X	X	X	X	X
Biopsy	X										
Cystoscopy	X										
TUR/re-TUR	X										
QOL assessment		X									
Administration of BC-819		X	X	X	X	X	X	X	X	X	X

Abbreviations: BC-819 = recombinant DNA plasmid complexed with polyethylenimine; ECOG = Eastern Cooperative Oncology Group; QOL = quality of life; re-TUR = repeat transurethral resection; TUR = transurethral resection; V = visit.

This document is confidential.

Table 2 Maintenance Treatment Through Visit 23 (Week 48)

Visit	V11	V12	V13	V14	V15	V16	V17	V18	V19	V20	V21	V22	V23
Week	12 Day 84	15	18	21	24	27	30	33	36	39	42	45	48
Interim physical examination including ECOG performance status	X	X	X	X	X	X	X	X	X	X	X	X	X
Vital signs	X	X	X	X	X	X	X	X	X	X	X	X	X
Complete blood count and biochemical profile	X				X								X
Urine sample for urinalysis (routine and microscopic)	X				X								X
Urine sample for culture and sensitivity	X				X								X
Adverse events	X	X	X	X	X	X	X	X	X	X	X	X	X
Concomitant medications	X	X	X	X	X	X	X	X	X	X	X	X	X

This document is confidential.

Maintenance Treatment Through Visit 23 (Week 48)

Visit	V11	V12	V13	V14	V15	V16	V17	V18	V19	V20	V21	V22	V23
Week	12 Day 84	15	18	21	24	27	30	33	36	39	42	45	48
Mandatory response assessment for patients with CIS	X				X ^a				X ^a				X ^a
Urine sample for cytology (must be completed within 14 days prior to BC-819 administration)	X				X				X				X
Cystoscopy (must be completed within 14 days prior to BC-819 administration)	X				X				X				X
TUR/re-TUR/biopsy as clinically indicated	X				X				X				X
QOL assessment				X								X	
Administration of BC-819	X	X	X	X	X	X	X	X	X	X	X	X	X

^a Mandatory in patients who have not previously achieved a CR in their baseline CIS.

Abbreviations: BC-819 = recombinant DNA plasmid complexed with polyethylenimine; CIS = carcinoma in situ; ECOG = Eastern Cooperative Oncology Group; QOL = quality of life; re-TUR = repeat transurethral resection; TUR = transurethral resection; V = visit.

This document is confidential.

Table 3 Maintenance Treatment Through Visit 39 (Week 96)

Visit	V24	V25	V26	V27	V28	V29	V30	V31	V32	V33	V34	V35	V36	V37	V38	V39/E OS
Week	51	54	57	60	63	66	69	72	75	78	81	84	87	90	93	96
Interim physical examination including ECOG performance status	X	X	X	X	X	X	X	X	X	X	X	X	X	X	X	X
Vital signs	X	X	X	X	X	X	X	X	X	X	X	X	X	X	X	X
Complete blood count and biochemical profile								X								X
Urine sample for urinalysis (routine and microscopic)								X								X
Urine sample for culture and sensitivity								X								X
Adverse events	X	X	X	X	X	X	X	X	X	X	X	X	X	X	X	X
Concomitant medications	X	X	X	X	X	X	X	X	X	X	X	X	X	X	X	X
Urine sample for cytology (must be completed within 14 days prior to BC-819 administration)				X				X				X				X

This document is confidential.

Statistical Analysis Plan for Phase I/II Oncology Studies

Sponsor: Anchiano Therapeutics Israel Ltd., Protocol No.: BC-819-18-204

Cystoscopy (must be completed within 14 days prior to BC-819 administration)				X				X				X					X
TUR/re-TUR/biopsy as clinically indicated				X				X				X					X
Administration of BC-819	X	X	X	X	X	X	X	X	X	X	X	X	X	X	X	X	

Abbreviations: BC-819 = recombinant DNA plasmid complexed with polyethylenimine; ECOG = Eastern Cooperative Oncology Group; EOS = end of study; re-TUR = repeat transurethral resection; TUR = transurethral resection; V = visit.

This document is confidential.

5. Endpoints

5.1 Efficacy Endpoints

5.1.1 Primary Efficacy Endpoint

The primary efficacy endpoint is, in patients with CIS at baseline, the:

- Proportion that achieves a CR at any time on or after week 12

Complete response is defined as at least one of the following:

- Negative cystoscopy and negative (including atypical) urine cytology
- Positive cystoscopy with biopsy-proven benign or low-grade NMIBC and negative cytology
- Negative cystoscopy with malignant urine cytology if cancer is found in the upper tract or prostatic urethra and random bladder biopsies are negative

The complete response in patients with CIS for this endpoint must be documented on or after the Week 12 response assessment. Duration of complete response in patients with CIS will be calculated from the documented onset of the complete response to the assessment where the patient no longer meets the definition of complete response. More generally, recurrence is defined as the reappearance or persistence of high-grade disease, or new high-grade disease. Recurrence must be biopsy proven. Persistence, appearance, or presence of lower grade disease will not be considered recurrence.

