### **PRIMARY EFFICACY ENDPOINT:**

The primary efficacy endpoint is, in patients with CIS at baseline, the:

- Proportion that achieves a complete response anytime on or after 12 weeks and within the first 48 weeks

Complete response in patients with CIS is defined as at least one of the following:

- Negative cystoscopy and negative (including atypical) urine cytology
- Positive cystoscopy with biopsy-proven benign or low-grade NMIBC and negative cytology
- Negative cystoscopy with malignant urine cytology if cancer is found in the upper tract or prostatic urethra and random bladder biopsies are negative

The complete response in patients with CIS for this endpoint must be documented on or after the Week 12 response assessment and on or prior to the Week 48 assessment. Duration of complete response in CIS patients will be calculated from the documented onset of the complete response to the assessment where the patient no longer meets the definition of complete response. More generally, recurrence is defined as the reappearance or persistence of high-grade disease or new high-grade disease including CIS.

Recurrence must be biopsy proven. Persistence, appearance, or presence of lower grade disease will not be considered recurrence.

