## 11. EFFICACY AND SAFETY ASSESSMENTS

### 11.1 Primary Efficacy Variable

The primary efficacy endpoint is, in patients with CIS at baseline, the:

- Proportion that achieves a CR at any time on or after week 12 and within the first 48 weeks

Complete response is defined as at least one of the following:

- Negative cystoscopy and negative (including atypical) urine cytology
- Positive cystoscopy with biopsy-proven benign or low-grade NMIBC and negative cytology
- Negative cystoscopy with malignant urine cytology if cancer is found in the upper tract or prostatic urethra and random bladder biopsies are negative

The complete response in patients with CIS for this endpoint must be documented on or after the Week 12 response assessment and on or prior to the Week 48 assessment. Duration of complete response in patients with CIS will be calculated from the documented onset of the complete response to the assessment where the patient no longer meets the definition of complete response. More generally, recurrence is defined as the reappearance or persistence of high-grade disease, or new high-grade disease. Recurrence must be biopsy proven. Persistence, appearance, or presence of lower grade disease will not be considered recurrence.

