### **13.5 Efficacy Analysis**

#### **13.5.1 Primary Efficacy Analysis**

The primary endpoint of the study is the CR rate in patients with CIS, supported by duration of the complete response.

A CR in patients with CIS is defined as at least one of the following:

- Negative cystoscopy and negative (including atypical) urine cytology
- Positive cystoscopy with biopsy-proven benign or low-grade NMIBC and negative cytology
- Negative cystoscopy with malignant urine cytology if cancer is found in the upper tract or prostatic urethra and random bladder biopsies are negative

The complete response in patients with CIS for this endpoint must be documented on or after the Week 12 response assessment and on or prior to the Week 48 assessment. The durability of the CRs will be described using Kaplan-Meier Plots of the duration of CR in responders. Duration of complete response in patients with CIS will be calculated from the documented onset of the complete response to the assessment where the patient no longer meets the definition of complete response. More generally, Recurrence is defined as the reappearance or persistence of high-grade disease or new high-grade disease. Recurrence must be biopsy proven. Persistence, appearance, or presence of lower grade disease will not be considered recurrence. Sensitivity analyses for duration of response will be performed starting from the time the CIS lesion clears to time that new CIS lesions are identified, censoring patients with no CIS but other high-grade disease at the time of recurrence and a separate analysis looking at the time from response until any NMIBC is found (including low-grade disease).

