7.3.1 Primary Efficacy Analysis

The primary endpoint of the study is the CR rate in patients with CIS, supported by duration of the CR.

A CR in patients with CIS is defined as at least one of the following:

- Negative cystoscopy and negative (including atypical) urine cytology
- Positive cystoscopy with biopsy-proven benign or low-grade NMIBC and negative cytology
- Negative cystoscopy with malignant urine cytology if cancer is found in the upper tract or prostatic urethra and random bladder biopsies are negative

The CR in patients with CIS for this endpoint must be documented on or after the Week 12 response assessment. Duration of CR in patients with CIS will be calculated from the documented onset of the CR to the assessment where the patient no longer meets the definition of CR. The durability of the CRs will be described using Kaplan-Meier plots of the duration of CR in responders. A tabular summary will also be created showing the proportion of patients with baseline CIS who are in response at 12, 24, 36, 48, 72 and 96 weeks using Kaplan-Meier estimates incorporating censoring (note that any patient who achieves response within 4 weeks of the planned assessment will be considered to be in response at that assessment, ie, a patient who has CR at 16 weeks will be a responder at 12 weeks). A similar tabular

This document is confidential.

summary will be created in the subset of patients with CIS who achieve a CR, that remain in response 12, 24, 36, 48, 52, 60, 72 and 84 weeks after the onset of response, for this summary, two methods will be used one which incorporates censoring and a second where patients who leave the study without losing response are considered failures. A by-patient swim lane plot of the time to CR and duration of CR in patients with CIS who respond will also be created. A similar summary will be created for the EFS (in all patients).

Sensitivity analyses for duration of response will be performed starting from the time the CIS lesion clears to time that new CIS lesions are identified, censoring patients with no CIS but other high-grade disease at the time of recurrence and a separate analysis looking at the time from response until any NMIBC is found (including low-grade disease).

A listing of CR rate and duration of response will be provided.

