7.7 Changes to Methods Planned in the Protocol

There are no changes from the analysis planned in the protocol.

This document is confidential.

8. Tables, Listings, And Figures

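### The SAP omits the protocol's Week 48 limit from the primary complete-response endpoint while declaring no change; few patients could be affected, but the two definitions must be made to agree

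*SAP*

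**What the plan says.** The protocol sets an upper time limit on the primary endpoint in three places.

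- Synopsis, primary efficacy endpoint: "Proportion that achieves a complete response anytime on or after 12 weeks and within the first 48 weeks".
- Section 11.1: "Proportion that achieves a CR at any time on or after week 12 and within the first 48 weeks". It then adds that the response "must be documented on or after the Week 12 response assessment and on or prior to the Week 48 assessment".
- Section 13.5.1 repeats the documentation window: "on or after the Week 12 response assessment and on or prior to the Week 48 assessment".

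The SAP has matching sentences that stop at the lower limit.

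- Section 5.1.1, endpoint: "Proportion that achieves a CR at any time on or after week 12".
- Section 5.1.1, documentation: "The complete response in patients with CIS for this endpoint must be documented on or after the Week 12 response assessment".
- Section 7.3.1: "The CR in patients with CIS for this endpoint must be documented on or after the Week 12 response assessment".

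No other part of the SAP restores the Week 48 limit for this endpoint. SAP 7.7 states: "There are no changes from the analysis planned in the protocol".

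**The concern.** The SAP governs the programming, and a programmer following 5.1.1 and 7.3.1 would write no Week 48 cutoff. Both documents schedule cytology and cystoscopy at Weeks 60, 72, 84 and 96, so a first CR could be recorded after Week 48 and would be counted.

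Two consequences follow. The denominator (treated patients with baseline CIS) is fixed, so widening the window can add responders but never remove them. And without an upper limit, patients with longer follow-up at the cutoff have more chances to qualify, so the rate depends on when the data are cut.

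The endpoint matters. Protocol 7.5 presents the single-arm CR rate as possible primary evidence for a marketing application. The trial is open-label with local pathology only. An undeclared difference in the favourable direction, beside a statement that nothing changed, invites a challenge to prespecification even if few patients are involved.

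**Working it through.** **1. The two definitions side by side**

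| | Protocol Synopsis, 11.1, 13.5.1 | SAP 5.1.1, 7.3.1 |
|---|---|---|
| Earliest qualifying CR | Week 12 assessment | Week 12 assessment |
| Latest qualifying CR | Week 48 assessment | none stated (last scheduled assessment is Week 96) |
| First CR at Week 60, 72, 84 or 96 | does not count | counts |

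**2. Who could have a first CR after Week 48**

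- *CIS not cleared at Week 12.* Protocol 9.6 and the Synopsis allow continued cystoscopy but class these patients as non-responders in the primary efficacy analysis. SAP 3.1 also classes persistent CIS at Week 12 or at later 12-week assessments as non-response. This is not a route to a late CR.
- *Positive cystoscopy, negative biopsy.* A benign or low-grade biopsy with negative cytology already meets the second CR criterion, so most such patients would qualify by Week 48 under both documents.
- *Malignant cytology with an upper-tract or prostatic-urethra source.* With negative cystoscopy and negative random biopsies this already meets the third CR criterion.
- *What remains.* Mainly, a patient with positive cytology through Week 48, negative biopsies and no source found elsewhere, who is still on study and first turns negative at Week 60 or later. Recurrence must be biopsy-proven, so such a patient need not have been discontinued.

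**3. The plan's own figures**

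Inputs from SAP 7.1.5: null rate 0.20, exact binomial test, two-sided 0.05, 70 to 100 CIS patients. The interval is Clopper-Pearson (Protocol Synopsis, statistical analysis). The lower limit for r responders of n is the 0.025 quantile of Beta(r, n − r + 1). The smallest r whose lower limit exceeds 0.20 is 22 at n = 70 and 29 at n = 100.

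- n = 70, true rate 0.40: P(X ≥ 22) = 94.5%. The plan says over 95%, so this is marginally lower.
- n = 100, true rate 0.35: P(X ≥ 29) = 91.5%. The plan says approximately 92%, which agrees.

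These calculations use only n and the two rates. They contain no time window, so restoring the limit leaves them unchanged.

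**4. What one extra CR does**

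| Responders | Observed rate | Lower 95% limit |
|---|---|---|
| 21/70 | 30.0% | 19.6% |
| 22/70 | 31.4% | 20.9% |
| 28/100 | 28.0% | 19.5% |
| 29/100 | 29.0% | 20.4% |

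One responder is 1/70 = 1.4 points or 1/100 = 1.0 point. It changes the reading against 20% only if the Week 48 count is exactly one short of the boundary. Under the plan's alternatives:

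- n = 70, rate 0.40: P(X = 21) = P(X ≥ 21) − P(X ≥ 22) = 96.8% − 94.5% = 2.3%.
- n = 100, rate 0.35: P(X = 28) = P(X ≥ 28) − P(X ≥ 29) = 94.4% − 91.5% = 2.9%.

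**5. Illustration under an assumed late-CR rate**

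The documents give no such rate. Assume the true CR rate by Week 48 is exactly 20% and late first CRs add x points. The chance that the lower limit exceeds 20% is then P(X ≥ r) at a rate of 0.20 + x.

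| x (assumed) | n = 70, r = 22 | n = 100, r = 29 |
|---|---|---|
| 0 | 1.6% | 2.0% |
| 1 point | 2.7% | 3.6% |
| 2 points | 4.3% | 6.2% |
| 3 points | 6.6% | 9.8% |
| 5 points | 13.6% | 20.8% |

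Five points is 3.5 patients of 70 or 5 of 100. Given step 2, the upper rows are the more plausible ones.

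**The case against.** The best defence is that the gap is nearly empty in practice. The non-responder classification removes the largest group, and the three CR criteria absorb most patients with negative biopsies. The rule in SAP 5.1.2 that repeated positive tests with negative biopsies are not treatment failure concerns EFS and says nothing about CR. Under SAP 7.1.3, a clear Week 60 after a missed Week 48 could be attributed back to Week 48. The row of mandatory CIS response assessments in SAP Table 2 ends at Week 48, and Table 3 has no such row, which fits the protocol's window. Any exact binomial endpoint can be tipped by one patient at its boundary, and SAP 7.3.1 states no success threshold.

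All of this stands as a limit on size. It also answers a stronger reading that a reader might infer: that patients who fail to clear CIS but continue under cystoscopy could later become primary-endpoint responders. The text that permits that follow-up also classes them as non-responders.

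None of it supplies the missing limit. Cytology and cystoscopy continue to Week 96, the schedule does not define the endpoint, and the SAP's endpoint wording remains open-ended.

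**Conclusion.** The inconsistency is real and concerns the primary endpoint. The SAP's window is wider than the protocol's, and SAP 7.7 is incorrect on this point. Any effect goes one way, upward, and depends on the cutoff.

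Its size is probably small. It rests on a narrow group of patients whose frequency the documents do not give. It could change a conclusion only at the boundary, and that boundary assumes the 20% null rate from the power statement is the success bar. No sample-size or power figure is affected.

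A reader might also infer that the endpoint was widened deliberately, or that the primary result is likely to be reversed. The documents support neither. They do not show whether the omission was intended, and they give no rate of late first CRs. The reason to act is that the primary endpoint must have one definition before the analysis.

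**What to change.** In SAP 5.1.1 and 7.3.1, adopt the protocol's documentation window: "on or after the Week 12 response assessment and on or prior to the Week 48 assessment". Apply that date condition in the primary CR derivation, and report any later first CR separately from the primary rate. SAP 7.7 is then true for this endpoint.

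If the open window is intended, declare and justify it in SAP 7.7 and align the Synopsis, 11.1 and 13.5.1 of the protocol before the analysis.

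While doing this, reconcile the Week 12 discontinuation and non-responder rule with the schedule-table footnote that makes response assessments at Weeks 24, 36 and 48 mandatory in patients without an earlier CR.

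The first option costs a phrase in two SAP sections and one date condition in the program. The second also needs a protocol amendment. Neither needs more patients or new data collection.
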